### **Informed Consent**

8. Capable of giving signed informed consent as described in [Section 10.1.3](#), which includes compliance with the requirements and restrictions listed in the informed consent form (ICF) and in this protocol.

## **5.2. Exclusion Criteria**

Participants are excluded from the study if any of the following criteria apply:

### **Medical Conditions**

1. History or presence of/significant history of or current cardiovascular, respiratory, hepatic, renal, gastrointestinal, endocrinological, hematological, or neurological disorders, or psychiatric disorder. Any surgical or medical history which may significantly alter the absorption, metabolism, or elimination of drugs or constitute a risk when taking the study intervention; or interfering with the interpretation of data (eg, gastric bypass, cyclical vomiting, etc).
2. History or presence of gastrointestinal conditions including chronic constipation and irritable bowel syndrome
3. Supine blood pressure  $\leq 90/60$  mmHg or  $> 140/90$  mmHg at Screening and on vital signs assessed prior to enrollment (Day -7); systolic or diastolic components outside of range should result in exclusion. Supine blood pressure should be taken after a minimum of 5 minutes in supine position. If vital signs are abnormal, two additional readings will be

taken. The mean of the 3 replicates will be recorded in the case report form (CRF) and used to determine inclusion.

4. Lymphoma, leukemia, or any malignancy except for basal cell or squamous epithelial carcinomas of the skin that have been resected with no evidence of metastatic disease for 3 years.
5. Breast cancer within the past 10 years
6. Alanine aminotransferase (ALT), aspartate aminotransferase (AST) or total bilirubin > upper limit of normal (ULN) of laboratory reference range at screening and at check-in (Day -8). At the discretion of the Investigator, a single repeat analysis may be performed per time point to assess eligibility. ALT, AST, and total bilirubin values on Day -1 must not exceed 1.3 x ULN to initiate ALXN1840 dosing on Day 1.
7. Serum Cu or serum ceruloplasmin below lower limit of normal on laboratory reference range at Screening
8. History of anemia or hemoglobin < 130 g/L for men and hemoglobin < 115 g/L for women at screening and at check-in (Day -8). At the discretion of the Investigator, a single repeat analysis may be performed per time point to assess eligibility.
9. History of benign ethnic neutropenia or absolute neutrophil count < 1500/uL; lymphocyte count below 1000/uL at check-in (Day -8). At the discretion of the Investigator, a single repeat analysis may be performed per time point to assess eligibility.
10. Blood donation or blood loss in excess of 500 mL in the 60 days prior to screening
11. ECG showing 120 ms > PR > 240 ms, QRS > 110 ms, and QTcF > 450 ms for men and QTcF > 480 ms for women at Screening and on Day -7 prior to enrollment. As with vital signs, if ECG interval measurements are abnormal, an additional 2 replicate measures will be performed with the mean of the 3 measured interval values used to confirm eligibility and recorded in the CRF.
12. Current or chronic history of liver disease or known hepatic or biliary abnormalities (except for asymptomatic gallstones). Participants with elevated total bilirubin or history of Gilbert's will be excluded from the study.
13. Any other significant disease or disorder which, in the opinion of the Investigator, may put the participant at risk or confound the interpretation of the results.
14. History of hypersensitivity to ALXN1840 or its excipients or any significant allergic reaction (eg, anaphylaxis or angioedema) to any product (eg, food, pharmaceutical).

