## 5. STUDY POPULATION

Prospective approval of protocol deviations to recruitment and enrollment criteria, also known as protocol waivers or exemptions, is not permitted.

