#### Type of Participant and Disease Characteristics

2. Participants who are healthy as determined by medical evaluation with no clinically significant or relevant abnormalities as determined by medical history, physical examination, vital signs, 12-lead ECG, and clinical laboratory evaluation (hematology, biochemistry, coagulation, and urinalysis) that are reasonably likely to interfere with the participant's participation in or ability to complete the study, or to potentially confound interpretation of study results, as assessed by the Investigator.
3. Have regular bowel movements (at least once per day)
4. Adequate venous access in the left or right arm to allow collection of study-required blood samples.
5. Willing and able to adhere to all dietary requirements of the study.

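### The PR limit in ECG exclusion criterion 11 is an inequality that no PR interval can meet, and the criterion does not say how its limits combine

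*Protocol*

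**What the plan says.** Protocol Section 5.2, criterion 11, excludes a participant for "ECG showing 120 ms > PR > 240 ms, QRS > 110 ms, and QTcF > 450 ms for men". It goes on to give the limit for women and the time points: "QTcF > 480 ms for women at Screening and on Day -7 prior to enrollment". It then adds a replicate rule: "if ECG interval measurements are abnormal, an additional 2 replicate measures will be performed", with the mean of the three readings used to settle eligibility.

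Four other places bear on how this is read.

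- The lead-in to Section 5.2: "Participants are excluded from the study if any of the following criteria apply". This governs how the numbered criteria combine with each other. It does not say how the parts of one criterion combine.
- Criterion 3 (blood pressure) does state its internal rule: "systolic or diastolic components outside of range should result in exclusion". Criterion 11 has no such sentence.
- Inclusion criterion 2 requires "no clinically significant or relevant abnormalities as determined by medical history, physical examination, vital signs, 12-lead ECG" and other evaluations, as assessed by the investigator. It gives no ECG figures.
- Section 5 opens with: "Prospective approval of protocol deviations to recruitment and enrollment criteria, also known as protocol waivers or exemptions, is not permitted".

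**The concern.** A chained inequality is shorthand for two conditions that must both hold. Written with 120 on the high side and 240 on the low side, it describes no PR interval at all. The three interval limits are then joined by *and*, and the two visits are joined by another *and*, without any statement of whether one abnormal interval, or one abnormal visit, is sufficient.

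Criterion 11 is the only place in Section 5 where ECG eligibility is given in numbers. Protocol Section 4.2 describes the study as the first repeat-dose study in healthy participants. Section 6.6.1.4 suspends an individual's dosing at a QTcF above 500 ms, and under Section 6.6.1.6 one participant meeting an individual rule leads to a Safety Review Committee meeting. An ECG entry rule therefore matters to participant safety and to the running of the study. The replicate rule in criterion 11, repeated in Section 8.2.3, uses mean intervals to confirm eligibility, so it depends on the same limits.

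**Working it through.** The plan gives no figure to reproduce. The check is one of logic, with a count to show how much the reading matters.

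**Step 1: the PR limit alone.** As written it requires PR < 120 and PR > 240. Any value above 240 is also above 120, so no value meets both. Over whole milliseconds from 60 to 400, 0 of 341 values qualify. If the intent was PR outside 120 to 240 ms (an assumption, since the protocol does not say so), the qualifying values would be 60 to 119 (60 values) and 241 to 400 (160 values), 220 in all.

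**Step 2: the whole criterion under four readings.** The grid is PR 60 to 400 ms by 1 (341 values), QRS 60 to 200 ms by 5 (29 values) and QTcF 350 to 600 ms by 5 (51 values), giving 341 × 29 × 51 = 504,339 combinations per sex. On this grid:

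- QRS > 110 holds for 18 values and fails for 11.
- QTcF > 450 (men) holds for 30 values and fails for 21.
- QTcF > 480 (women) holds for 24 values and fails for 27.

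| Reading | Men: combinations excluded | Women: combinations excluded |
|---|---|---|
| A. PR as written, all limits required | 0 | 0 |
| B. PR outside 120–240, all limits required | 220 × 18 × 30 = 118,800 | 220 × 18 × 24 = 95,040 |
| C. PR as written, any one limit sufficient | 504,339 − 341 × 11 × 21 = 425,568 | 504,339 − 341 × 11 × 27 = 403,062 |
| D. PR outside 120–240, any one limit sufficient | 504,339 − 121 × 11 × 21 = 476,388 | 504,339 − 121 × 11 × 27 = 468,402 |

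Here 121 = 341 − 220, the PR values inside the range. These are counts of grid points, not participant rates. They show only that the readings differ. The gap between C and D is what the void PR limit loses if the list reading is right: 220 × 11 × 21 = 50,820 combinations for men and 220 × 11 × 27 = 65,340 for women, all with an abnormal PR and nothing else abnormal.

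**Step 3: single cases.** Does criterion 11 exclude the participant?

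| Participant (PR / QRS / QTcF, ms) | A | B | C | D |
|---|---|---|---|---|
| Man, 150 / 90 / 520 | no | no | yes | yes |
| Man, 300 / 90 / 400 | no | no | no | yes |
| Woman, 150 / 130 / 400 | no | no | yes | yes |
| Man, 100 / 120 / 460 | no | yes | yes | yes |

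The second row shows that reading the limits as a list does not rescue the PR limit. The first row shows that repairing the PR inequality alone does not settle the criterion: with *and* kept as a conjunction, an isolated QTcF of 520 ms still does not meet it.

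**The case against.** The strongest reply is that nobody would read the sentence as a strict conjunction. The same clause joins the QTcF limit for men to the QTcF limit for women with *and*. No participant can meet both as a man and as a woman, so that word must be a list connector. Criterion 8 sets out its sex-specific hemoglobin limits in the same style. On that reading the QRS and QTcF limits each exclude. This stands. A reader might infer from the literal text that criterion 11 excludes nobody, but that is the result of one reading, and not the natural one. It leaves the PR limit untouched, because that limit is void on both readings.

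A reader might also infer that someone with an abnormal ECG has no other barrier to enrollment. The documents do not support that. Inclusion criterion 2 and exclusion criteria 1 and 13 allow exclusion on clinical judgment. Table 2 schedules a triplicate ECG before the Day 1 dose, and Section 7.1 has the investigator decide on continuation after a clinically significant finding. These safeguards are real, although none of the eligibility criteria among them gives an ECG figure.

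Three further inferences go too far.

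- The bar on waivers does not make the literal reading govern. It forbids approving departures from the criteria and is silent on how an unclear criterion is read. It is only a reason for wanting a rule that can be applied as it stands.
- Inconsistent classification between sites is not a supported risk, because SAP Section 7.3.1.3 marks multicenter considerations not applicable. Different investigators, monitors or auditors could still differ.
- The two-visit *and* is not peculiar to criterion 11. Criteria 3, 6 and 8 have it too, and the documents do not state that an abnormal result at either visit excludes.

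**Conclusion.** The point holds for the PR limit without any assumption: as written, it can exclude no one. It also holds that criterion 11 does not state how its interval limits or its two visits combine, whereas criterion 3 states its own rule for components. Whether the rest of the criterion works depends on the reading. It is empty as a strict conjunction. As a list, which is probably the intent, the QRS and QTcF limits work and only PR is lost.

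This is a wrongly stated threshold in an operative safety eligibility rule, not a matter of missing detail. The practical effect is probably limited, since staff are likely to infer the intent and judgment-based exclusion remains available. The zero is a logical result. It does not estimate how many people would be wrongly enrolled, and the documents give no basis for such an estimate. No effect on the copper-balance endpoint or its analysis has been shown.

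**What to change.** The sponsor should amend criterion 11 in three respects:

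1. Correct the PR inequality so that it can be met, using the sponsor's own existing limits.
2. State explicitly whether any one interval out of range is enough to exclude.
3. State how the Screening and Day -7 results combine, reconciled with the two-visit wording of criteria 3, 6 and 8 so that all four follow a declared rule.

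The sponsor's medical lead should confirm both the limits and the rule. No limit or visit rule is proposed here. The cost is one sentence at the next amendment, with no change to sample size, procedures or analysis.

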#### **Prior/Concomitant Therapy**

15. Use or intended use of prescription medications (excluding oral contraceptives) within 14 days or 5 half-lives of the drug (whichever is longer) prior to Day -7, and/or intended use at any point over the duration of the study except with prior approval of Alexion.
16. Use of nonprescription/ over-the-counter medications, including herbal remedies and supplements, within 7 days or 5 half-lives of the drug (whichever is longer) prior to Day -7 and/or intended use at any point over the duration of the study.

**Prior/Concurrent Clinical Study Experience**

17. Exposure to more than 4 new chemical entities within 12 months prior to dosing
18. Current enrollment or past participation, within the last 90 days, before signing of consent in this or any other clinical study involving an investigational study intervention or any other type of medical research. Participants, involved in intervention studies using investigation or non-investigational drug with prolonged half-lives, are not eligible unless the time since last treatment has exceeded 90 days or 5 half-lives of the study intervention, whichever is longer. Those who participated in the non-interventional Cu/Mo balance test study C19029 conducted by Richmond Pharmacology Limited (RPL), London, the United Kingdom between 17 Oct 2019 and 27 Oct 2019 are eligible to participate in this study.

**Diagnostic Assessments**

19. Presence of hepatitis B surface antigen or positive hepatitis C antibody or RNA test result at screening or within 3 months prior to first dose of the study intervention.  
NOTE: Patients with positive Hepatitis C antibody due to prior resolved disease can be enrolled if a confirmatory negative Hepatitis C ribonucleic acid (RNA) test result is obtained. NOTE: The RNA test is optional and patients with negative Hepatitis C antibody test are not required to also undergo Hepatitis C RNA testing
20. Positive human immunodeficiency virus (HIV) antibody test

**Other Exclusions**

21. Female participants who are pregnant, as evidenced by a positive serum pregnancy test result at screening, or breastfeeding.
22. Prior exposure to ALXN1840.
23. Major surgery or hospitalization within 90 days prior to dosing on Day 1.
24. Use of tobacco in any form (eg, smoking, chewing or vaping), other nicotine-containing products in any form (eg, gum, patch, electronic cigarettes, or vapes), or any recreational inhalational product within 6 months prior to the planned first day of dosing.
25. Use of known drugs of abuse within 6 months prior to the planned first day of dosing.
26. History of significant alcohol abuse within 1 year prior to the screening visit, or clinical evidence of substance and/or alcohol abuse within the 2 years before screening. Alcohol abuse is defined as regular weekly intake of more than 14 units (for both males and females), using the following NHS alcohol tracker <http://www.nhs.uk/Tools/Pages/drinks-tracker.aspx>.
27. Positive urine drug toxicology screen at Screening or on Day -8.
28. Alcohol consumption within 24 hours prior to study intervention administration or positive alcohol breath test at screening or on Day -8.
29. Sensitivity to any of the study interventions, or components thereof, or drug or other allergy that, in the opinion of the investigator or Medical Monitor, contraindicates participation in the study.

### 5.3. Lifestyle Considerations

Participants must be able and willing to adhere to the lifestyle restrictions detailed in [Table 4](#).

**Table 4: Healthy Participant Lifestyle Considerations**

Restrictions	Timeframe restriction applies	Restrictions end

Food Participants will remain on a Cu/Mo controlled diet. Standardized Cu- and Mo-controlled meals will be provided as described in the SoA (Table 1). Male participants will receive larger meals than female participants, with adequate meal size to ensure appropriate daily caloric intake. If a participant is unable to eat 100% of the food, the remaining food will be weighed and reported in the CRF to support Cu/Mo determination as a fraction of the total meal. Participants will be expected to fast overnight. During the dosing period (Day 1 through Day 15), participants will be administered ALXN1840 with 240 mL of water each morning; participants must remain fasted for a least 2 hours after dose administration.
 
Participants must allow for collection of all stool and urine from Day -4 through Day 30)
	Dietary restrictions will remain in place from Day -7 through Day 30	Participants may return to routine diet after completion of Day 30.

Fluids All participants will drink water from the same large water bottle dispenser. There will be no set maximum volume of water that the participants must consume, but there will be a minimal volume that they must consume each day (1.5 L). The precise volume that each participant consumes will be measured.
	Water restrictions will remain in place from Day -7 through Day 30	Participants may return to routine fluid intake after completion of Day 30.
Tobacco in any form (eg, smoking or chewing), other nicotine-containing products in any form (eg, gum, patch, electronic cigarettes), or any recreational inhalational product.	From Screening to EOS visit.	Restrictions ends after completion of EOS visit.
Not consume any other substances known to be potent inhibitors or inducers of CYP450s. This includes food or drink products containing cranberry, pomegranate, star fruit, grapefruit, pomelos, exotic citrus fruits or Seville oranges (including marmalade and juices made from these fruits). Red wine should also not be consumed.	Within 7 days before check-in to the CRU (Day -8) until discharge on Day 31.	After discharge from the CRU.
Caffeine-containing or xanthine-containing products (eg, tea, coffee, cola drinks, and chocolate).	During each dosing period, 24 hours before check-in to the CRU (Day -8) through Day 30.	After collection of the final PK sample for the study (Day 30).
Energy drinks or drinks containing taurine, glucuronolactone (eg, Red Bull).	48 hours before check-in to the CRU (Day -8) through EOS visit.	Restrictions ends after completion of EOS visit.

Restrictions	Timeframe restriction applies	Restrictions end
Alcohol	48 hours before check-in to the CRU (Day -8) and until discharge (Day 31), and 48 hours before each study outpatient/Follow-up Visit.	Discharge from the clinical research unit and completion of EOS visit.
Physical Activity Participants will carry out daily scheduled light exercise. This is to help encourage regular bowel movements and for health benefits to the participants.  Participants must refrain from strenuous activity four 24 hour prior to each for the duration of the study.	48 hours prior to check-in to the CRU (Day -8) and until discharge (Day 31).	Restrictions ends after completion of EOS visit.
Any prescription medication. Concomitant prescription medications may be used during the study to treat adverse events as deemed medically indicated by the investigator. The investigator or delegate will notify the Sponsor of any adverse events requiring administration of prescription medication(s) while on study. Note: Investigator in consultation with the Sponsor should determine participant's continued suitability to remain in the study.	14 days or 5 half-lives (whichever is longer) prior to Day -7 through EOS visit.	Restrictions ends after completion of EOS visit.
Any nonprescription/over-the-counter medication, including herbal remedies and supplements. For details, Section 6.5.1 .	Nonprescription/over-the-counter medications may be used for adverse events under the direction and at the discretion of the investigator including up to 1000 mg/day of paracetamol/acetaminophen.	After the EOS visit.
Any herbal remedy or dietary supplement containing St John's Wort.	2 weeks before the planned first study intervention is administered.	After EOS visit.
Blood and plasma donation	Blood donation or blood loss in excess of 500 mL in the 60 days prior to screening ( Section 5.2 )	1 month after EOS visit.
Contraception: Participants must consistently and correctly use one or more of the appropriate contraceptive methods described in Section 10.4 .	Start times for contraceptives vary according to method used (see inclusion criteria #7).	See Section 10.4 .

Abbreviations: CRF = case report form; CRU = clinical research unit; Cu = copper; CYP450 = cytochrome CYP450; EOS = end of study; Mo = molybdenum; PK = pharmacokinetic.

## 5.4. Screen Failures

Screen failures are defined as participants who consent to participate in the clinical study but are not subsequently assigned to study intervention. A minimal set of screen failure information is required to ensure transparent reporting of screen failure participants to meet the Consolidated Standards of Reporting Trials (CONSORT) publishing requirements and to respond to queries from regulatory authorities. Minimal information includes demography, screen failure details

(eg, failed eligibility criteria), and any AEs, including any serious adverse events (SAEs) and any related concomitant medication, occurring during the screening period.

Individuals who do not meet the criteria for participation in this study (screen failure) due to a reason that is expected to resolve or has resolved, may be rescreened based on discussion and agreement between the Investigator and the Medical Monitor.

## 6. STUDY INTERVENTION

Study intervention is defined as any investigational intervention(s), marketed product(s), placebo, or medical device(s) intended to be administered to a study participant according to the study protocol.

### 6.1. Study Intervention Administered

Details of ALXN1840 administered in the study are provided in [Table 5](#).

**Table 5: Details of Study Intervention Administered**

Arm Name	Study Intervention
Intervention Name	ALXN1840 (formerly WTX101)
Type	Drug
Dose Formulation	Tablet
Unit Dose Strength(s)	15 mg ALXN1840 containing 7.8 mg of tetrathiomolybdc acid
Dosage Level(s)	Repeat dose 30 mg administered as 2 × 15 mg ALXN1840 tablets for 15 days
Route of Administration	Oral
Use	experimental/study intervention
IMP and NIMP	IMP
Sourcing	Provided centrally by Alexion
Packaging and Labeling	The labeling of study intervention will be in compliance with Good Manufacturing Practice specifications, as described in the Rules Governing Medicinal Products in the European Union, Volume 4, annex 13, Investigational Medicinal Products, and any other or local applicable regulations. Sample labels will be submitted to the UK health authorities according to the submission requirements.
Current/Former Name(s) or Alias(es)	Bis-choline tetrathiomolybdate

Abbreviations: IMP = investigational medicinal product; NIMP = noninvestigational medicinal product.

### 6.2. Preparation/Handling/Storage/Accountability

1. The Investigator or designee must confirm appropriate temperature conditions have been maintained during transit for all study intervention received and any discrepancies are reported and resolved before use of the study intervention.
  - a. The ALXN1840 treatment kits should be stored at refrigerated conditions, 2°C to 8°C (36°F to 46°F).
2. Only participants enrolled in the study may receive the study intervention and only authorized site staff may supply or administer the study intervention. All study intervention must be stored in a secure, environmentally controlled, and monitored (manual or automated) area in accordance with the labeled storage conditions with access limited to the Investigator and authorized site staff.
3. The Investigator and/or qualified delegate (ie, Pharmacist) is responsible for study intervention accountability, reconciliation, and record maintenance (ie, receipt, reconciliation, and final disposition records).
  - a. This responsibility includes the reporting of any product complaints to PPD within 1 business day. A product complaint is defined as any written, electronic, or oral communication that alleges deficiencies

related to the identity, quality, durability, reliability, usability, safety, effectiveness, or performance of a product or clinical trial material and/or its packaging components after it has been released for distribution to an end customer that affects the performance of such product.

4. Further guidance and information for the final disposition of unused study interventions are provided in the Pharmacy Manual.

